1.0 Objectives / Specific Aims

The overall aim of this proposed effort is to test transcutaneous auricular neurostimulation (tAN) as a therapeutic for opioid withdrawal and neonatal abstinence syndrome (NAS).

We hypothesize that tAN delivered for up to 60 minutes during peak withdrawal (1h before next morphine dose) will be safe, well tolerated and will decrease Finnegan withdrawal scores and shorten the length of morphine treatment compared with historical data.

Aim 1: Determine the safety and feasibility of auricular neurostimulation therapy in neonates with opioid withdrawal or NAS.

We hypothesize that auricular neurostimulation is safe and tolerable in both a single session, and 12-day treatment course. Furthermore, we believe target engagement can be validated by measuring stimulation-induced reductions in heart rate. Milestone: No adverse events of bradycardia (HR < 80 bpm), worsening of swallowing or feeding, skin irritation, or elevation of Neonatal Infant Pain Scores.

Aim 2: Demonstrate that auricular neurostimulation therapy in opioid withdrawing or NAS neonates reduces the Finnegan and/or WAT-1 scores from pre- to post-stimulation. We have used ear electrodes for taVNS in a similar stuy (#67997). However, in this prospective, open-label study we will use a novel, non-significant risk auricular neurostimulation device and ear electrodes to study 20 opioid withdrawing or NAS neonates at the Medical University of South Carolina. We aim to show a clinically-meaningful reduction in Finnegan scores, the routine assessment that includes 21 signs of withdrawal (Finnegan 1992). Alternatively, in infants who receive both opioids and benzodiazepine analgesics, we aim to show a clinically-meaningful reduction in Withdrawal Assessment Tool (WAT-1) scores, which is a validated, 11 item/12 point scale used to monitor opioid withdrawal in pediatric patients (Franck 2008). In the study, we will deliver up to 60 minutes of tAN 1 hour prior to each morphine administration, up to 4 times per day for up to 12 days. If morphine is weaned off at or before 10 days, a weaning phase for tAN will begin on the following day for 2 days: tAN Weaning Day 1: deliver tAN twice tAN Weaning Day 2: deliver tAN once We will assess each patient with standard Finnegan scores and/or WAT-1 before and after stimulation, and monitor use of morphine throughout the study. We expect a 25% reduction in Finnegan/WAT scores from before to after sessions of auricular neurostimulation.

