10.0 Study Design / Methods

After obtaining consent and describing this procedure to the parents and all members of the baby's care team, we will first deliver stimulation per our protocol in #67997 to determine the perceptual threshold. We will use the identical method for determining the intensity for PT, which has proven to be safe as in our taVNS study in infant feeding. We will start with 0.2mA with a 250µs, 5Hz in vagus and 100Hz in trigeminal nerve area, and gradually increase the intensity of the TENS unit until the baby can first feel something in their ear. We will use the facial expression change, fidgety movements to determine when the infants feel the stimulation, as in the taVNS study. This intensity will be recorded as the **perceptual sensory threshold (PT)**. The procedure is detailed below.

Determination of Perceptual Threshold

- 1. Electrode clip will be placed on the left tragus in an enrolled infant at rest. Starting at 0.2mA at 5Hz in vagus and 100Hz in trigeminal nerve area, we will deliver 5 seconds of pulses, and increase by 0.1mA until the perceptual threshold is achieved by observation of the infant's facial expression, fidgety movements. This will be termed the perceptual threshold.
- 2. We will decrease the microcurrent by $\sim 0.1 \text{mA}$ below the perceptual threshold and administer this as the taVNS treatment dose 1h before the morphine dose and before the infant is feeding, every 3h, for 60 minutes, up to 4 times per day. Current will then be held constant while pulse width and frequency will be set at $250 \mu \text{s}$ and 5 Hz in vagus area and 100 Hz in trigeminal nerve area, respectively.
- 3. Finnegan scores will be rated before and immediately after the taVNS treatment, and per usual clinical protocol. WAT-1 scores will also be rated during tAN treatment per usual clinical protocol.
- 4. Physiological data will be monitored continuously as measured by the echocardiogram (ECG).
- 5. Neonatal Infant Pain Scale (NIPS) data collected at beginning and the end of treatment session. The NIPS rating scale currently in use in the nursery is included in this submission.

taVNS Protocol

These studies will be conducted in the Shawn [name] Children's Hospital's Neonatal Intensive Care Unit (NICU).

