Participants will receive tAN stimulation to their left ear via electrodes attached to the ear. The stimulation intensity we will use for tAN will be ~0.1mA less than PT or each infant. We will recalibrate the PT daily, and then deliver that current intensity for each session that day administered every 3h, starting 1h before the morphine dose. The current will be on for 5 minutes, off for 10 seconds, for up to 60 minutes total each session, up to 4 times per day, for up to 12 days or until morphine is weaned off. If morphine is weaned off at or before 10 days, a weaning phase for tAN will begin on the following day for 2 days. tAN Weaning Day 1: deliver tAN twice. tAN Weaning Day 2: deliver tAN once.

The nurses will score the NAS using the Finnegan scale before and after the treatment. The Withdrawal Assessment Tool (WAT-1) will also be used to assess infant withdrawal symptoms before and after treatment in infants receiving benzodiazepines and opioids (Franck 2008, 2013). The WAT-1 is an 11 item/12 point scale to monitor withdrawal and is routinely performed by nurses 3 times per 12 hour shift with hands on care.

Prior to beginning the study, Drs. [name] and [name] will perform an in-depth in service with the charge nurses of the neonatal nurseries, a limited pool of 10 nurses. They will also in-service the neonatal nurses at their staff meetings to introduce them to the study, the rationale, the protocol and the equipment. Most nurses are familiar with ear electrode stimulation from the taVNS-paired feeding study conducted over the past 18 months.

A short developmental test, the STEP, will be performed while the infant is stil in the nursery and at the first neonatal high-risk developmental clinic (outpatient) follow-up visit.

Safety Monitoring

Prior to determination of the daily sensory threshold of the infant by the study coordinator or research assistant, an initial pain level will be recorded using the NIPS. The nurse or other staff may decrease the current intensity or stop stimulation entirely if the infant shows signs of distress or an increase in NIPS score >3 above baseline. As opioid withdrawing infants frequently have higher NIPS, we will only halt or adjust stimulation if the NIPS is 3 greater than their baseline. The nursing staff routinely measure and record the NIPS throughout the day. We will monitor the relationship of increased NIPS scores to the up to 60 minute stimulation period daily.

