15.0 Risks to Subjects

tAN is another form of taVNS using transcutaneous electrical nerve stimulation (TENS) of the auricular branches of the vagus and trigeminal nerves that innervate the ear. Although this novel therapeutic modality is still in the development and optimization process, risks are a combination of those to be expected by both the peripheral TENS and taVNS, which has been safely used in neonates and infants at MUSC by the study team: Heart rate decrease, discomfort and skin irritation.

Theoretical risks associated with neuromodulation of the parasympathetic nervous system via taVNS would also be applicable in the administration of noninvasive tNS, including reduction of heart rate. In the taVNS study we observe a transient 10% decrease of baseline HR with onset of stimulation and rapid rebound within 60 seconds. We have seen no epsidsodes of bradycardia related to taVNS stimulation and expect none in this protocol.

TENS devices are FDA approved for pain relief and are available over the counter. The main risks associated with TENS is that stimulation may result in discomfort. The unit used in this studies is an FDA 510(k) cleared electrical stimulator that meets the rigorous electrical standards of the FDA. Skin irritation, redness, or inflammation may occur under the stimulating electrodes if TENS current is delivered for a prolonged period of time, but is not expected with up to 60 minutes of stimulation, similar to the duration of taVNS in protocol #67997.

Given the minimal risk both of these already FDA approved methods, we expect tAN like taVNS, will be a very safe procedure.

Risk of loss of confidentiality: We will assign study numbers to each participant, keep CRF and consent forms in locked cabinets in locked offices. Database files with names and contact information will be password protected and stored on the MUSC Pediatric server. All other data files related to this study will be identified by participant number only, without link to standard identifiers. We will publish the aggregate data only.

Unknown Risks: TENS stimulation of peripheral nerves is FDA approved and is considered very safe. Although tAN is essentially TENS on the ear, it is still an experimental procedure that has not been approved by the FDA to improve outcome of infants with opioid withdrawa symptoms. Therefore, there may be risks and discomforts that we are not aware of.

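### Neither the threshold ramp nor the halt rule makes a heart rate below 80 bpm a reason to stop stimulation, although it is one of the protocol's own Aim 1 safety events

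*Protocol*

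**What the plan says.** **Ramp.** Section 10.0, Determination of Perceptual Threshold, step 1, starts at 0.2 mA with 5-second bursts, and the operator is to "increase by 0.1mA until the perceptual threshold is achieved by observation of the" infant's facial expression and fidgeting. The treatment current is about 0.1 mA below the level found. The taVNS Protocol text adds "We will recalibrate the PT daily", and that day's current is then used for every session. The section opens by deferring to another study: "we will first deliver stimulation per our protocol in #67997 to determine the perceptual threshold".

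**Halt rule.** Under Safety Monitoring in the same section, staff may lower or stop the current for signs of distress or for a NIPS rise of more than 3. The next sentence, which opens by noting that these infants often have raised scores, says "we will only halt or adjust stimulation if the NIPS is 3 greater than their baseline".

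**Heart rate.** Section 1.0, Aim 1, expects that "target engagement can be validated by measuring stimulation-induced reductions in heart rate" and sets as a milestone "No adverse events of bradycardia (HR < 80 bpm"), among other events. Section 15.0 names heart rate decrease as a risk and reports: "In the taVNS study we observe a transient 10% decrease of baseline HR with onset of stimulation". Section 10.0, step 4, provides the signal: "Physiological data will be monitored continuously as measured by the echocardiogram (ECG"). No action is attached to it.

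**The concern.** The protocol expects stimulation to lower heart rate, treats a rate below 80 bpm as a safety failure, and has the monitor running. The two written rules that govern current, however, respond only to what an observer sees or scores. An infant whose heart rate falls below 80 bpm without distress or a NIPS rise meets no written reason to interrupt the ramp or the session.

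Participant safety is at stake under an aim whose subject is safety. Interruption would depend on the judgement of whoever is at the bedside, and the response could differ between shifts. No bias in an efficacy comparison is claimed. Dose-setting and stopping instructions are protocol content, so a statistical analysis plan that is not shown would not be expected to supply them.

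**Working it through.** The protocol gives no figure to reproduce. The check sets the rules side by side, then does a little arithmetic on heart rate.

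**1. What each provision triggers**

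| Protocol provision | Signal used | Written action | Heart rate named? |
|---|---|---|---|
| 10.0, step 1 (ramp) | Face, fidgeting | Ramp ends | No |
| 10.0, Safety Monitoring | Distress, NIPS rise | May reduce or stop | No |
| 10.0, Switching ears | Redness or other medical need at the site | Use other ear | No |
| 10.0, Estimated Difficulties | As needed | Current can be lowered | No |
| 10.0, step 4 | Continuous ECG | None | Implied by ECG |
| 1.0, Aim 1 | HR < 80 bpm | None (milestone event) | Yes |
| 15.0 | HR decrease | None (risk statement) | Yes |

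The provisions that name or measure heart rate carry no action, and those that carry an action do not name heart rate.

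**2. Timing of the signals.** Step 5 takes NIPS at the start and end of a session. Section 4.0 speaks of scores during treatment, and Safety Monitoring says nurses score through the day, but no time within a session is fixed. The scored trigger may therefore not be assessed mid-session, while the continuous signal triggers nothing.

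**3. How far heart rate would have to fall.** Inputs are the 80 bpm limit (Section 1.0) and the 10% transient fall seen in the taVNS study (Section 15.0). The protocol gives no baseline heart rate, so 120 and 140 bpm are assumptions.

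- Baseline from which a 10% fall reaches 80 bpm: 80 / 0.90 = 88.9 bpm.
- Fall needed from 120 bpm: (120 − 80) / 120 = 33.3%.
- Fall needed from 140 bpm: (140 − 80) / 140 = 42.9%.

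The reported stimulation effect alone would seldom cross the limit at these baselines. This does not cover background dips. Section 5.0 says short, mostly self-resolving falls are common in preterm infants, and it excludes only infants with repeated episodes that do not self-resolve.

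**4. How often the rules are used (upper bounds).** Ramps: 20 infants × 12 days = 240. Sessions: 20 × 12 × 4 = 960, fewer where treatment ends early or is being weaned. These count uses of the rules and do not measure harm.

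**5. The ramp with no reaction.** After k steps the current is 0.2 + 0.1k mA. Step 1 gives no upper limit for k and no instruction if nothing is seen. In that case neither threshold nor treatment dose is defined.

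**The case against.** **The word *only* is not a ban.** A reader might infer that the NIPS sentence forbids stopping for bradycardia. The document does not support that. The sentence explains why the score is judged against the infant's own baseline. The sentence before it already gives distress as a separate trigger, other text allows the current to be lowered as needed, and Section 14 ends sessions at once if a parent withdraws the infant from treatment. The list is therefore not exhaustive. This objection stands in full: the trigger is unwritten, not prohibited.

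**A ceiling may exist elsewhere.** A reader might also infer that the current can rise without limit. Section 10.0 adopts the method of #67997, and a cap there would come in by reference. The pulse generator will also have some maximum output, though none is stated. This stands as far as it goes. The carry-over is unconfirmed, because #67997 used an ear clip (Section 1.0) and this device is a four-electrode earpiece (Section 3.0), while step 1 still speaks of a clip. What can be said is that no limit is restated here, which is missing detail and not a demonstrated exposure.

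**Practical risk is low.** Infants are on cardiorespiratory monitors, Section 15.0 reports no bradycardia related to taVNS, and neonatal staff would probably respond. Signs of distress are undefined and might be read to include bradycardia. All of this lowers the risk, but it leaves the response to discretion.

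**A bare stop at 80 bpm would be too blunt.** It would end sessions for brief dips that Section 5.0 treats as compatible with stability. This is correct, and it is why the remedy should be a pause with a restart rule.

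**Conclusion.** The point holds in a limited form. The protocol's written rules for ending the ramp and for halting a session do not include bradycardia, although the protocol names the risk, sets the 80 bpm limit and monitors the signal. This rests on the text alone and needs no assumption about what #67997 or the device specification contains.

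Its size cannot be estimated. The document shows no harm, no rate of non-reaction and no frequency of background dips. The 240 ramps and 960 sessions are not evidence of harm. Nor does the arithmetic show that a trigger at 80 bpm would be rare, since it addresses only the reported 10% effect. The 33.3% and 42.9% figures depend on assumed baselines.

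The change is worth making because it is cheap, uses the protocol's own threshold and needs no new monitoring. The missing maximum current and no-reaction instruction are secondary, and alone would be only missing detail.

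**What to change.** **Main change, in Section 10.0, step 1 and Safety Monitoring.** Require stimulation, in the ramp or a session, to be paused whenever heart rate falls below 80 bpm, and the event to be recorded as an Aim 1 safety event. Resume at the same or a lower current once heart rate has recovered. End the session if the fall recurs or does not self-resolve.

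**Secondary change, in step 1.** Restate the maximum current confirmed for this earpiece, from the device specification or from #67997. No value is proposed here, because the protocol gives none. State that an infant with no reaction by that maximum has no threshold recorded and is not treated that day.

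**Cost.** A few protocol sentences, using monitoring already in place. Some sessions will be paused for brief, self-resolving dips unrelated to stimulation, at an unknown frequency. The resume rule limits the lost treatment. A non-reacting infant would miss a day of treatment.

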5.0 Inclusion and Exclusion Criteria/ Study Population

Inclusion criteria: Neonates or infants with opioid withdrawal or NAS who have withdrawal scores requiring morphine replacement therapy. They must be clinically stable, on minimal respiratory support (Continuous positive airway pressure (CPAP), nasal cannula, or room air), >33 weeks gestational age at enrollment, and currently receiving replacement therapy for opioid dependence.

Exclusion criteria:

- 1) Unstable infants or those requiring significant respiratory support.
- 2) Repeated episodes of autonomic instability (apnea or bradycardia) which are not self-resolving *
- 3) Infants <33weeks gestation at enrollment.
- 4) Major unrepaired congenital anomalies
- 5) Cardiomyopathy

*Preterm infants commonly have short periods of shallow or absent breathing or lower heart rate termed apnea and bradycardia, respectively, and most are being treated for these physiologic manifestations of prematurity with caffeine, an effective central stimulant. Infants are on cardiorespiratory monitors through the nursery stay with recording devices to capture events and play them back. However, nearly all of these events are self resolving, meaning the infant resolves the breathing pause or bradycardia on their own. Infants who require repeated episodes of stimulation to come out of these events are defined as *unstable*. Similarly, infants on significant respiratory support are not stable, and will not be eligible.

Stable neonates who are dependent on opioids, such as after ECMO, severe illness or brain injury, will be included in this study, as these neonates represent a population in which tAN could minimize withdrawal while not adding to burden of pharmacotherapies. Congenital syndromes may be included if the infants do not have major, unrepaired anomalies.

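### The bedside rule for reducing or stopping stimulation is stated twice, with two NIPS cut-offs and two sets of triggers

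*Protocol*

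**What the plan says.** The rule stands in Protocol section 10.0, under Safety Monitoring, in two consecutive sentences.

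- The first permits the nurse or other staff to lower the current or switch it off "if the infant shows signs of distress or an increase in NIPS score >3 above baseline".
- The second reads: "As opioid withdrawing infants frequently have higher NIPS, we will only halt or adjust stimulation if the NIPS is 3 greater than their baseline".

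Other parts of the protocol bear on it:

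- Section 1.0, Aim 1, names bradycardia, defined as HR < 80 bpm, among the adverse events that the safety milestone requires to be absent. NIPS elevation is in the same list.
- Section 10.0 gives the timing of the study pain scores: "Neonatal Infant Pain Scale (NIPS) data collected at beginning and the end of treatment session". Safety Monitoring adds: "The nursing staff routinely measure and record the NIPS throughout the day".
- On heart rate, section 10.0 says "Physiological data will be monitored continuously", and section 5.0 says "Infants are on cardiorespiratory monitors through the nursery stay with recording devices to capture events".
- Section 10.0, under Estimated Difficulties, gives nurses an on/off switch and the means to lower the current when needed.
- Section 13.0 makes the investigators responsible for reviewing adverse events and limiting risk.
- Section 15.0 lists a fall in heart rate as a risk. It reports a transient 10% fall in the earlier taVNS study, with rebound within 60 seconds, and no stimulation-related bradycardia.

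No section says what to do with the current if HR falls below 80 bpm.

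**The concern.** A rule for switching off the current in a neonate should give one answer for one infant. Here two staff members could act differently in the same situation and each cite the protocol. The NIPS cut-off differs between the sentences. Distress is a trigger in the first and missing from the second, which is worded as exclusive. The heart-rate event in the safety milestone appears in neither.

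Safety and tolerability are Aim 1, and nurses, including those on night shift, operate the device. What can vary is whether current is reduced, whether a session is completed, and so how much stimulation lies behind the tolerability results. A bedside rule of this kind belongs in the protocol itself and is not a detail left to an analysis plan.

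**Working it through.** The protocol gives no figure to reproduce. The check sets the two sentences side by side.

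**Step 1: the NIPS cut-off.** The first sentence needs a rise greater than 3. The second needs a score 3 above baseline, taken here as a rise of at least 3. Assuming whole-point scoring:

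- first sentence: rise > 3, so the minimum is 4
- second sentence: rise ≥ 3, so the minimum is 3

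They disagree at a rise of exactly 3 and nowhere else on the scale.

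**Step 2: the triggers, case by case.**

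| Situation | First sentence | Second sentence, literal | Second sentence, read as setting a relative NIPS cut-off |
|---|---|---|---|
| Rise of 4 or more | may act | act | act |
| Rise of exactly 3, no distress | no trigger | act | act |
| Rise of exactly 3, with distress | may act | act | act |
| Distress, rise below 3 | may act | barred | silent; first sentence governs |
| HR < 80 bpm, rise below 3 | may act only if this counts as distress, which is not stated | barred | silent; first sentence governs, with the same doubt |

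The conflict in row 2 remains on both readings of the second sentence. The conflicts in rows 4 and 5 depend on the literal reading.

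**Step 3: how often the rule could be consulted.** The maximum is 4 sessions per day × 12 days = 48 sessions per infant, and 48 × 20 infants = 960 sessions. This is a ceiling on exposure to the rule. It does not count sessions in which the sentences disagree, and that number cannot be derived from the protocol.

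**Step 4: would naming HR < 80 bpm interrupt sessions for the expected response?** A 10% fall reaches 80 bpm only from a baseline of 80 / 0.90 = 88.9 bpm. The protocol gives no baseline heart rate, so a range is assumed:

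| Assumed baseline (bpm) | After a 10% fall: baseline × 0.90 | Fall needed to reach 80: (baseline − 80) / baseline |
|---|---|---|
| 100 | 90 | 20.0% |
| 120 | 108 | 33.3% |
| 140 | 126 | 42.9% |
| 160 | 144 | 50.0% |

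Over this range the expected transient fall stays above 80 bpm, so the added trigger would not normally fire because of it.

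**The case against.** The best defence is that the second sentence explains the first. Its opening clause, on the high pain scores of withdrawing infants, gives the reason for judging NIPS against the infant's own baseline. On that reading *only* limits the NIPS criterion and leaves distress in force. This is probably what was meant, and it stands against the literal reading of rows 4 and 5. It does not remove the difference at a rise of exactly 3. It also asks bedside staff to infer that a written restriction on stopping was not intended.

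A reader might infer that NIPS is the sole trigger, and a poor one because the study scores are scheduled at the beginning and end of a session of up to 60 minutes. The protocol does not support this: the preceding sentence names distress separately, and routine nursing scores continue through the day.

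A reader might also infer that bradycardia would go unseen or unmanaged. That does not follow either. Heart rate is monitored continuously, nurses can lower or switch off the current, the investigators review adverse events, and infants with repeated episodes that do not resolve on their own are excluded. What is missing is an explicit link between HR < 80 bpm and the current, which is mostly a matter of detail.

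Finally, the Aim 1 milestone counts bradycardia and NIPS elevation without reference to the stopping cut-off. No effect on an endpoint or analysis has been shown, and that part of the objection stands in full.

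**Conclusion.** The stop/adjust rule is inconsistent as written and no other section resolves it. The firm part is one point on the NIPS scale: a rise of exactly 3 in an infant without distress, or a minimum rise of 4 against 3 if scoring is in whole points. The second part, that *only* excludes distress and HR < 80 bpm as reasons to stop, holds only on a literal reading that was probably not intended. Even so, the text should not allow it.

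This is a minor to moderate wording error in a safety rule. How often either conflict would arise cannot be derived: the protocol gives no distribution of NIPS changes, and section 15.0 expects no bradycardia.

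**What to change.** Replace the two sentences with one rule, for example:

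> Staff may decrease or stop the current for signs of distress (including HR < 80 bpm during stimulation) or for a NIPS rise of at least 3 above baseline. Because baseline NIPS is often high in these infants, the NIPS criterion refers only to the rise from baseline.

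The investigators may prefer a rise of more than 3, provided one cut-off is used throughout. Whether to add steps for pausing and resuming, and any time limit, is best left to them. The 60-second figure in section 15.0 describes rebound from a 10% fall and not recovery from bradycardia. The distinction in section 5.0 between self-resolving events and unstable infants defines eligibility and is not a rule for managing events during a session.

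The cost is a short amendment and one line in the nurse in-service already planned; the heart-rate data are already on the monitor. The downside is that a few sessions may be interrupted by events unrelated to stimulation. Section 5.0 describes short apnea and bradycardia as common in preterm infants, although "nearly all of these events are self resolving, meaning the infant resolves the breathing pause or bradycardia on their own". Recording the reason for each interruption would keep the feasibility counts interpretable.

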4.0 Study Endpoints

Safety Outcomes: 1) Skin irritation, assessed by staff daily. 2) NIPS pain scores recorded during treatment.

Efficacy Outcomes: 1) Finnegan scores before and after tAN will be recorded at each session or WAT-1 scores will be recorded with hands on care . 2) Duration of morphine weaning. 3) Length of stay We will also collect data on developmental outcomes from a short motor test in the nursery and from routine clinic visits to the NICU high-risk follow-up clinic up to 24months.

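### The two halt/adjust sentences in Safety Monitoring conflict, and the NIPS-only version leaves infants with baselines near the scale maximum with no reachable trigger

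*Protocol*

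**What the plan says.** The rules stand in consecutive sentences of the protocol, section 10.0 Study Design / Methods, Safety Monitoring.

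- **Sentence A** permits staff to lower the current or stop "if the infant shows signs of distress or an increase in NIPS score >3 above baseline".
- **Sentence B** follows directly: "As opioid withdrawing infants frequently have higher NIPS, we will only halt or adjust stimulation if the NIPS is 3 greater than their baseline".

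The same paragraph says that, before the daily threshold is determined, "an initial pain level will be recorded using the NIPS". This appears to be the baseline that both sentences refer to.

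The range of the scale is not printed. Item 5 of the threshold procedure in section 10.0 says: "The NIPS rating scale currently in use in the nursery is included in this submission". The same item has NIPS collected at the start and the end of each session.

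NIPS also enters the safety results. Section 4.0 lists "NIPS pain scores recorded during treatment" as one of two safety outcomes, and the Aim 1 milestone in section 1.0 calls for no adverse events of several kinds, including "skin irritation, or elevation of Neonatal Infant Pain Scores".

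**The concern.** Bedside nurses will apply this rule, and the two sentences give them different instructions. Sentence A offers two routes, distress or a NIPS rise. Sentence B, through the word *only*, offers one.

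The conflict matters most in infants who start high. A rule based on a fixed rise needs room above the baseline, and a bounded scale has little room near its top. The protocol's reason for using a rise is "As opioid withdrawing infants frequently have higher NIPS", and a higher baseline is exactly what uses up that room. If sentence B governs, an infant who starts near the maximum can be visibly distressed without meeting any condition for halting or adjusting. If sentence A governs, the distress route covers that infant and the *only* in sentence B is wrong. The text does not say which governs.

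Correcting only the difference between more than 3 and 3 would leave both the distress question and the ceiling in place.

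**Working it through.** The protocol gives no figure of its own to reproduce here. The check has two parts.

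**1. The two sentences side by side**

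NIPS is taken in whole points, and *3 greater* is read as a rise of at least 3.

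| Situation | Sentence A | Sentence B |
|---|---|---|
| Distress, NIPS rise below 3 | may reduce or stop | no halt or adjustment |
| No distress, rise of exactly 3 | condition not met | condition met |
| No distress, rise of 4 or more | may reduce or stop | condition met |

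The sentences differ in the first two rows and agree in the third.

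**2. Which baselines can reach the trigger**

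Inputs:
- Required rise k: k = 3 under sentence B; k = 4 under the NIPS part of sentence A, because more than 3 in whole points means at least 4. Both are from section 10.0, Safety Monitoring.
- Scale maximum M: not in the text available. Assumption: a whole-point scale from 0 to M, shown for M = 6, 7, 8 and 10.

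Formula: from baseline b the largest possible rise is M − b. A rise of at least k is possible only if M − b ≥ k, that is, b ≤ M − k. Baselines from M − k + 1 to M, which are k score values, cannot reach the trigger.

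| Assumed M | Cannot reach a rise of 3 (b > M − 3) | Cannot reach a rise of more than 3 (b > M − 4) | Cannot rise at all (b = M) |
|---|---|---|---|
| 6 | 4–6 | 3–6 | 6 |
| 7 | 5–7 | 4–7 | 7 |
| 8 | 6–8 | 5–8 | 8 |
| 10 | 8–10 | 7–10 | 10 |

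Whatever M is, the top three score values cannot trigger under sentence B, and the top four cannot trigger under the NIPS part of sentence A. The last column shows that a smaller rise stays possible everywhere except at the maximum itself. With M = 7, an infant starting at 5 can go to 6 or 7, a rise of 1 or 2 points. That does not meet either NIPS condition, but it appears in the start and end scores.

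**The case against.** The strongest reply is that sentence B was never meant to cancel the distress route. On that reading, *only* qualifies the NIPS criterion and explains why a change is used instead of an absolute level. Section 10.0, under Estimated Difficulties, supports this: nurses have an on/off control and can turn the current down when needed. This reading is plausible, and under it high-baseline infants keep a route to halting. The wording does not say so, however, and the two sentences also differ on the size of the rise, so the need to reconcile them remains.

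A second reply is that the practical reach is unknown. That stands. The protocol says higher scores are frequent, not that scores near the maximum are frequent. It gives no baseline distribution, and the cut-offs above depend on an assumed maximum.

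A reader might go further and infer that sessions starting near the ceiling can only count as showing no elevation, so that the tolerability result is biased. The documents do not support this:

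- The Aim 1 milestone gives no size for an elevation and does not refer to the 3-point rule.
- The milestone is an absence of adverse events. It is not a proportion of sessions, so there is no denominator to inflate.
- Rises of 1 or 2 points remain visible below the maximum. Only a baseline exactly at the maximum can show no rise.

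Setting such sessions aside as not assessable would therefore remove real elevations in infants who start with high scores.

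**Conclusion.** The point holds in a limited form. Sentences A and B conflict on whether distress alone suffices and on whether a rise of exactly 3 counts. The NIPS condition cannot be met from the top three score values (sentence B) or the top four (sentence A). Read literally, sentence B leaves infants with those baselines without any trigger, and the protocol's own rationale for the rule points towards such baselines.

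The count of three or four blind values needs only a bounded whole-point scale. The specific cut-offs depend on M, which is assumed here and which the sponsor can read off the scale sheet. The share of infants or sessions affected cannot be computed from the protocol and may be small. No bias in the Aim 1 milestone is shown.

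**What to change.** The clinical team should reconcile the two Safety Monitoring sentences into one rule that states:

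1. whether signs of distress are a sufficient reason to reduce or stop stimulation regardless of the NIPS score;
2. whether the NIPS condition is a rise of 3 or of more than 3;
3. how the rule operates when the baseline leaves no room for the stated rise.

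The form and level of the rule are theirs to set.

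In the safety results, keep the recorded start and end NIPS scores for high-baseline sessions with all the others, and do not exclude these sessions.

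The cost is a rewording of one or two sentences in section 10.0 and the same wording in the nurse in-service. No new data, visits or infants are needed.
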